### 9.4.2.2 Intratumoral Injection of Lesions

The intratumoral injection of ADU-S100 should only be performed by trained personnel. On dosing days where pembrolizumab is also administered, ADU-S100 should be administered following completion of the pembrolizumab infusion provided the subject is considered clinically stable.

All lesions designated for ADU-S100 administration should be injected on Days 1 and 8 of each dosing cycle (i.e. do not rotate/alternate sites for injection, all designated lesions will be injected on every dosing day unless repeat administration is no-longer possible, See [Section 9.4.2.3](#)). Confirm biopsy area has healed prior to initiating dosing.

ADU-S100 will be diluted as described in the Pharmacy Manual to achieve the assigned dose level prior to administration. An injection volume of 1.0 mL ADU-S100 dosing solution should be administered per lesion.

Local anesthetic may be used per institutional guidelines but should not be injected directly into the lesion. Injection of ADU-S100 should be conducted per institutional guidelines using sterile technique. Ultrasound-guided injection may be utilized per institutional guidelines. The best attempt should be made to distribute the entire volume of ADU-S100 throughout the lesion; multiple passes may be used. Record the start and stop times for each administration.

#### 9.4.2.3 Regression of Injected Lesions

If a lesion shows signs of significant regression (i.e. shrinkage) that precludes the ability to re-inject the lesion, other accessible lesions may be injected after documented discussion between the Investigator and the Medical Monitor.

If the injected lesion(s) shows signs of significant regression such that only scar tissue is remaining, a PET scan should be performed to identify whether any tumor tissue remains. If no tumor tissue remains, administration of ADU-S100 at the lesion may be discontinued.

After all lesions that meet requirements in [Section 9.4.2.1](#) have been successfully treated, additional smaller lesions may be injected with ADU-S100 following consultation with the Medical Monitor.

If the injected lesion(s) shows signs of significant regression (i.e. shrinkage) such that repeat administration of ADU-S100 is no longer possible in any lesion, the subject will be scheduled to complete the EOT visit and may continue treatment with pembrolizumab as monotherapy/standard of care outside the context of the ADU-CL-20 clinical trial. Previously resolved injected lesions that recur can be re-injected as long as the subject has not met criteria for treatment discontinuation ([Section 8.3.2](#)).

### 9.5 Dose Interruptions and Dose Modification for Treatment-related Toxicities

Dose interruptions are recommended for subjects who do not tolerate the protocol-specified dosing schedule. In the case of acute reaction to pembrolizumab infusion, the scheduled dose of ADU-S100 may be delayed (or withheld) following consultation with the Medical Monitor.

Following the first 4 cycles of study treatment, dosing interruptions are also permitted in the case of medical / surgical events, palliative radiation, or logistical reasons not related to study therapy (e.g. elective surgery, unrelated medical events, vacation, and/or holidays), after discussion with the Medical Monitor. Subjects should be placed back on study therapy within 3 weeks of the scheduled interruption, unless otherwise discussed with the Medical Monitor. The reason for interruption should be documented in the subject's study record.

**Pembrolizumab:** No dose reductions of pembrolizumab are recommended. Subjects who experience unacceptable toxicity directly attributable to pembrolizumab may continue on study and receive ADU-S100 as single agent study treatment with approval by the Medical Monitor.

**ADU-S100:** For subjects who experience systemic TEAEs with a suspected relationship to ADU-S100, the dose level of ADU-S100 may be reduced following sufficient resolution of the event (Section 9.5.1) and after consultation with the Medical Monitor.

General guidelines for ADU-S100 dose reduction:

- Reduce dose to 400 mcg/lesion
- If tolerability issues persist, the dose level may be further reduced to 200 mcg/lesion
- If tolerability issues persist at 200 mcg/lesion; discontinue ADU-S100 treatment

The following sections provide guidance for management of general and specific toxicities which may be associated with administration of pembrolizumab or ADU-S100.

### **9.5.1 General Toxicity and Dose Modification Guidelines**

Occurrence of any of the TEAEs outlined in [Table 9-2](#) requires dose modification and/or treatment discontinuation. No dose reductions of pembrolizumab are recommended. If discontinuation of pembrolizumab is warranted, a subject may continue on ADU-S100 monotherapy following consultation with the Medical Monitor ([Section 9.5.2](#)). If ADU-S100 is discontinued due to a Grade 4 injection site reaction, monotherapy with pembrolizumab should continue and the subject will complete the EOT visit and safety monitoring periods.

ADU-S100 dose reductions may be allowed following consultation with the Medical Monitor ([Section 9.5.3](#)).

**Table 9-2 Toxicities Requiring Dose Modification or Treatment Discontinuation**

Any Grade 4 AEs will lead to permanent treatment discontinuation with the exception of:
 
 
• Neutropenia lasting <math>\leq 5</math> days that is not associated with fever or other clinical symptoms
 
• Lymphopenia or leukopenia
 
• Electrolyte abnormalities not associated with clinical sequelae or deemed not clinically significant and are corrected with appropriate management or supplementation within 72 hours of onset
 

Drug Induced Liver Injury (DILI) will lead to permanent study treatment discontinuation as indicated by serum chemistry values consistent with Hy's Law criteria (all 3 of the following must co-exist):
 
 
• ALT or AST <math>\geq 3\times</math> institutional upper limit of normal (ULN)
 
• Total bilirubin <math>\geq 2\times</math> ULN
 
• Alkaline phosphatase <math>< 2\times</math> ULN
 

Grade 4 injection site reaction will lead to discontinuation of ADU-S100
Grade 3 or higher infusion-related reaction will lead to discontinuation of pembrolizumab

Any Grade 3 AEs may lead to dose modification or delay of either ADU-S100 or pembrolizumab after consultation with the medical monitor with the exception of:
 
 
• Serum lipase and/or serum amylase (asymptomatic) CTCAE Grade 3 <math>< 7</math> consecutive days
 
• Nausea and vomiting that resolves within 2 days after starting optimal anti-emetic therapy
 
• Thrombocytopenia without significant bleeding
 
• Anemia that resolves within 7 days in the absence of transfusion
 
• Diarrhea that resolves within 2 days after starting optimal anti-diarrhea treatment
 
• Hypertension that resolves within 7 days after starting treatment
 
• Infection or fever in the absence of neutropenia that resolves within <math>< 5</math> days
 
• Rash or photosensitivity that resolves within 7 days after starting treatment
 
• Fatigue that resolves within 7 days
 

Grade 2 or 3 clinically significant injection site reactions will lead to delay and/or dose modification of ADU-S100 (See Section 9.5.4 )
Grade 2 clinically significant immune-related toxicities, including a single event or multiple occurrences of the same event per investigator discretion may lead to discontinuation of pembrolizumab
Eye pain or reduction of visual acuity that does not respond to topical therapy and does not improve to Grade 1 severity within 2 weeks of the initiation of topical therapy OR requires systemic treatment may lead to discontinuation of pembrolizumab
Any immune related AE that meets criteria for discontinuation ( Appendix A )

The following general dose modification guidelines should be followed for AEs outlined in [Table 9-2](#) or other suspected study drug-related events:

- If a subject experiences an AE outlined in [Table 9-2](#) or other unacceptable toxicity, consult the Medical Monitor prior to resuming treatment
- Generally if a dose is interrupted or withheld for AE, treatment may be resumed following resolution of the AE to Grade 1 or baseline
  - If the Investigator considers it in the subject's best interest to resume treatment before the AE has resolved to Grade 1, the Medical Monitor should first be consulted.

- If dose interruptions persist > 6 weeks (from the expected day of dosing), the subject will be discontinued from the study treatment unless there is evidence of clinical benefit and the Investigator deems it is in the subject's best interest to remain on study. In such cases, the Medical Monitor must be consulted.
- ADU-S100 only: If a subject requires more than 2 dose interruptions for the same toxicity, ADU-S100 should be discontinued.

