**FOOTNOTES FOR TABLE 2-1 (See Sections 9 and 10 for additional information)**

 Cycle length is 21 days. If a dose of either study drug is delayed, shift scheduled assessments accordingly.

 EOT Visit occurs 30 days (+7 days) after the last dose of study drug (ADU-S100 or standard of care [pembrolizumab]) or prior to commencing new anti-cancer therapy.

 Safety Follow-up to complete required Safety Reporting Periods (Table 10-1), as indicated. Concomitant medications will only be collected if associated with the management of an ongoing AE or SAE, or if a new anti-cancer treatment. Following EOT, subject may be contacted by phone to complete SAE reporting period as applicable.

-  **Demographics, Medical History, Height:** includes date of birth, age, gender, ethnicity, and race. Medical history includes all active conditions and any condition considered to be clinically significant by the Investigator. Disease-specific details include date of diagnosis, primary tumor histology, prior surgery(ies), radiation therapy, chemo- and biological therapies, and stage of cancer. Obtain standing height.
-  **Tumor imaging:** See [Section 10.2.1](#). Collect scans electronically; perform response assessments per RECIST 1.1 and iRECIST. Tumor assessments should be fixed according to calendar, regardless of treatment delays. After 27 weeks, the imaging frequency for all subjects will be performed at a Q12W (-14 days) frequency until confirmed disease progression, withdrawal, or study end. Perform at EOT if more than 6 weeks have passed since last evaluation.
-  **Vital Signs:** Blood pressure, pulse, respiratory rate, and temperature. Cycles 1 and 2: scheduled time points relative to the start of the pembrolizumab infusion (Day 1) = pre-dose, end of infusion (+30 minutes); scheduled time points relative to the start of the ADU-S100 injection (Days 1, 8) = pre-dose, 3 hour ( $\pm 30$  minutes) and 6 hours ( $\pm 30$  minutes) post-dose. On all other dosing days, perform vital sign assessment prior to the start of each study drug or more frequently as clinically indicated.
-  **Physical Examination:** Complete physical examinations at Screening and EOT; all other indicated visits are symptom-directed physical examinations. Weight at each indicated visit. Assessment may be done up to 3 days prior to visit.

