#### **8.3.2 Discontinuation from Study Treatment**

A subject should be discontinued from treatment for any of the following reasons:

- Withdrawal of consent or subject requests study treatment discontinuation for any reason
- Occurrence of any medical condition or circumstance that exposes the subject to substantial risk and/or does not allow the subject to adhere to the requirements of the protocol
- Confirmed disease progression ([Section 10.2.1.1](#))

- Any unacceptable toxicity, SAE, clinically significant AEs, severe laboratory abnormality, intercurrent illness, or other medical condition which indicates to the Investigator that continued participation is not in the best interest of the subject
- Subject experiences any Grade 4 adverse event, with the exception of those listed in [Table 9-2](#)
- Pregnancy
- Subject failure to comply with protocol requirements or study-related procedures. [Dosing compliance issues should be reviewed on a case-by-case basis with Medical Monitor.]
- Termination of the study by the Sponsor or regulatory authority

Subjects who experience unacceptable toxicity directly attributable to pembrolizumab may continue on study and receive ADU-S100 as single agent study treatment with approval by the Medical Monitor.

If a subject's study treatment (ADU-S100 and/or pembrolizumab) is discontinued, this will not result in automatic withdrawal of the subject from the study. The Investigator will provide a reason for treatment discontinuation. Subjects who discontinue treatment will be encouraged to complete EOT and follow-up assessments.

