### 9.5.4 Guidelines for ADU-S100 Injection Site Reactions

The following guidelines are recommended for injection site reactions related to ADU-S100:

- Grade 1: Continue study treatment
- Grade 2: Delay study treatment until resolved to  $\leq$  Grade 1
- Grade 3: Delay study treatment until resolved to  $\leq$  Grade 1; resume treatment after consultation with the Medical Monitor
- Grade 4: Permanently discontinue ADU-S100 treatment.

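### Protocol Table 9-2 applies both a general Grade 4 stop rule and single-drug rules to Grade 4 injection-site and infusion reactions, and no passage says which governs

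*Protocol*

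**What the plan says.** Table 9-2 lists the toxicities that call for changing or stopping treatment. Its first row is general: "Any Grade 4 AEs will lead to permanent treatment discontinuation with the exception of" short uncomplicated neutropenia, lymphopenia or leukopenia, and electrolyte abnormalities that cause no clinical problem and are promptly corrected. The list ends there.

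Two later rows deal with specific reactions: "Grade 4 injection site reaction will lead to discontinuation of ADU-S100", and "Grade 3 or higher infusion-related reaction will lead to discontinuation of pembrolizumab". The detailed sections repeat these single-drug actions. Section 9.5.4 says "Grade 4: Permanently discontinue ADU-S100 treatment", and Section 9.5.3 stops pembrolizumab permanently for a Grade 3 or 4 infusion reaction.

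Section 9.5.1 then covers the other drug. Once ADU-S100 has been stopped for a Grade 4 injection-site reaction, "monotherapy with pembrolizumab should continue and the subject will complete the EOT visit and safety monitoring periods". For the opposite case, "If discontinuation of pembrolizumab is warranted, a subject may continue on ADU-S100 monotherapy following consultation with the Medical Monitor".

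Section 8.3.2 gives this among its reasons for stopping treatment: "Subject experiences any Grade 4 adverse event, with the exception of those listed in" Table 9-2.

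On the end-of-treatment (EOT) visit, Table 2-1 footnote 2 says "EOT Visit occurs 30 days (+7 days) after the last dose of study drug" and then names either drug. Section 10 times the visit from the last dose of ADU-S100 and/or pembrolizumab.

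**The concern.** A Grade 4 injection-site reaction falls under the first row of Table 9-2 and also under a later row of the same table. So does a Grade 4 infusion reaction. The later rows each name one drug to stop. The first row names none and does not except these reactions. A site with such a patient therefore has two applicable rules that can lead to different handling of the second drug.

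Three things depend on the answer:

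- whether the second drug is given after a life-threatening event;
- whether the subject counts as a treatment discontinuation under the >33% safety rule in Section 7.2.2, which refers back to Section 8.3.2;
- whether a subject with no response assessment enters the Evaluable Analysis Set (EAS) of Protocol Section 12.3 by the toxicity route.

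On-study or off-study status also matters for follow-up. The protocol's Table 2-1 has no visit column after EOT, so status decides whether scheduled scans continue and hence where progression-free survival is censored (Section 12.5.2).

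**Working it through.** The plan gives no figure to reproduce on this point, so the check is mainly a comparison of text.

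**Step 1. The rules side by side.**

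| Source | Grade 4 injection-site reaction | Grade 4 infusion reaction |
|---|---|---|
| Table 9-2, first row | treatment discontinued, no drug named, not excepted | same |
| Table 9-2, later rows | ADU-S100 stopped | pembrolizumab stopped |
| Sections 9.5.4 and 9.5.3 | ADU-S100 stopped | pembrolizumab stopped |
| Section 9.5.1 | pembrolizumab continues, EOT completed | ADU-S100 alone possible after consultation |

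**Step 2. Does Section 8.3.2 settle it?** Its exception can be read in three ways.

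- Only the exceptions listed in the first row. Both reactions are then reasons to stop treatment, and the conflict stands.
- Every entry in the table. The first row is itself an entry and covers any Grade 4 event, so the exception would swallow the rule.
- The first-row exceptions plus the rows for specific reactions. This would harmonise Section 8.3.2 with the later rows, but no passage states it, and the first row of Table 9-2 would still omit both reactions.

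**Step 3. On or off study under Section 9.5.1.** For lesion regression, Section 9.4.2.3 has the subject complete EOT and says that any further pembrolizumab is given outside the trial. For pembrolizumab toxicity, Section 8.3.2 says that the subject may stay on study with ADU-S100. Section 9.5.1 says neither for pembrolizumab continued after a Grade 4 injection-site reaction.

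The timing shows why this matters. ADU-S100 is given on Days 1 and 8 of a 21-day cycle and pembrolizumab on Day 1. Assume no delay to pembrolizumab.

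- Last ADU-S100 on Day 1: EOT falls on Day 1 + 30 = 31 to Day 1 + 37 = 38. The next pembrolizumab is due on Day 1 + 21 = 22.
- Last ADU-S100 on Day 8: EOT falls on Day 8 + 30 = 38 to Day 8 + 37 = 45. Pembrolizumab is due on Day 22, and again on Day 22 + 21 = 43.

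At least one pembrolizumab dose is therefore due before an EOT timed from ADU-S100. If that dose is on study, an EOT timed from the last dose of either drug moves later. If it is off study, it does not. The reporting windows in Table 10-1 also run from last doses.

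**Step 4. The Section 7.2.2 rule.** It applies above 33% of subjects, with no denominator stated. Two illustrations:

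- 20 subjects (the enrolment cap): 6/20 = 30.0%, not met; 7/20 = 35.0%, met.
- 16 subjects (treated by 17 December 2020, Section 5.2.2): 5/16 = 31.3%, not met; 6/16 = 37.5%, met.

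These show where the threshold lies. They do not measure how many subjects the conflict affects.

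**The case against.** The strongest reply is that the protocol leans clearly toward single-drug action. The later rows, Sections 9.5.3 and 9.5.4, and the monotherapy provisions in Sections 8.3.2, 9.5 and 9.5.1 all point that way, and a specific rule normally overrides a general one. That is a natural reading. It does not remove the problem, because no passage states the precedence and the first row's own exception list was the place to put it.

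Four stronger readings are tempting, and the documents do not support them.

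- A reader might infer that the first row plainly orders both drugs stopped. It names no drug, and Section 8.3.2 speaks of study treatment as ADU-S100 and/or pembrolizumab. The both-drugs reading is well supported, because the other rows name a drug when they mean one, but it remains a reading.
- A reader might infer that two compliant sites could manage the reaction itself in opposite ways. On every reading the drug implicated in the reaction is stopped, and only the second drug is in doubt. Section 9.5.1 also requires consultation with the Medical Monitor before treatment resumes after any Table 9-2 event. That limits divergence without correcting the text.
- A reader might infer that Section 9.5.1 contradicts the EOT definition. Section 10's and/or wording is compatible with EOT after ADU-S100 alone stops, and the lesion-regression text follows the same sequence. This part is an ambiguity.
- A reader might infer that seven discontinuations would stop the trial. The denominator is not given, and the rule prompts Safety Review Team evaluation within 72 hours, not an automatic stop.

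The situation is also probably rare. Sections 5.2.2 and 7.3 describe two earlier studies (47 and 102 subjects) and this trial. No Grade 4 injection-site or infusion reaction is named among the earlier studies' events, and the treatment-related serious events listed for this trial are all Grade 3. The Grade 4 list for the 102-subject study is introduced as examples, so it is only indicative.

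**Conclusion.** The main point holds. For the same Grade 4 reactions, the first row of Table 9-2 and the later rows state different rules, Sections 9.5.1, 9.5.3 and 9.5.4 follow the later rows, and Section 8.3.2 does not resolve the difference. The unstated status of pembrolizumab under Section 9.5.1 is a secondary ambiguity.

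The number of subjects affected cannot be derived from the documents and is probably small in a trial of up to 20. The effect on the Section 7.2.2 count depends on an unstated denominator and on whether stopping one drug counts. The effect on the EAS is confined to subjects with no evaluable response assessment. It does not change the primary analysis population in the SAP, because SAP Section 7.4.4 uses the All Treated Population and Section 7.4.5 repeats the response rate on the EAS. The point still deserves correction, because it concerns treatment after a life-threatening event and the remedy is cheap.

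**What to change.** Reconcile Sections 8.3.2, 9.5.1, 9.5.3, 9.5.4 and Table 9-2 so that each Grade 4 reaction has one stated consequence throughout. Which consequence applies is a clinical decision for the sponsor. The same wording should state:

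- which Table 9-2 entries the Section 8.3.2 exception covers;
- whether pembrolizumab continued under Section 9.5.1 is on or off study, and when EOT falls;
- whether stopping one drug counts as a treatment discontinuation under Section 7.2.2, and of how many subjects the 33% is taken;
- whether stopping one drug counts as discontinuation for toxicity in the EAS definition (Protocol Section 12.3, and the parallel definition in SAP Section 7.2).

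The cross-reference in Section 9.5.1 that sends the reader to Section 9.5.3 for ADU-S100 dose reduction can be corrected at the same time, since that section concerns pembrolizumab infusion reactions. The cost is a protocol clarification letter or a few lines of amendment text. No new data or assessments are needed.

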### 9.5.2 Management of Immune-related Adverse Events

AEs with suspected immunologic etiology, which may be severe or fatal, can occur in any organ system or tissue in subjects receiving immunotherapy. These immune-related AEs (irAEs) may occur after the first dose or several months after the treatment discontinuation. Suspected irAEs should be adequately evaluated to confirm etiology or exclude other causes; additional procedures or tests may be included as part of the evaluation.

Guidelines for dose modification and toxicity management for irAEs are provided in [Appendix A](#); additional recommendations are provided in the American Society of Clinical Oncology clinical practice guideline for the management of irAE ([Brahmer et al. 2018](#)).

Consult the current prescribing information for any updates to dose modification language for irAE or infusion reactions.

### 9.5.3 Guidelines for Pembrolizumab Infusion-related Reactions

Per approved product label ([KEYTRUDA 2020](#)) the following guidelines are recommended for infusion-related reactions associated with pembrolizumab:

- Grades 1 or 2: Interrupt or slow the rate of infusion
- Grades 3 or 4: Discontinue pembrolizumab permanently

